#### **12.4.2 Vital Signs and ECG Changes**

Vital signs data (HR and BP) will be presented as summary statistics of maximum (max) absolute values, max change from baseline, and time to max value during the 1-hour period after each cocaine infusion. Data will be compared between groups and within groups by study day by Wilcoxon rank sum statistic. Effects will be considered statistically significant at a two-sided  $p < 0.05$ . In addition, summary statistics for vital signs at each study time point will also be presented. Changes in ECG intervals during saline infusion as compared to those taken during cocaine infusions will be reported as summary statistics. Clinically significant ECG changes will be presented as counts and percentages.

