## **12.6 Subjective Assessment Analyses (VAS and BSCS)**

Subjective effects VAS will be presented as summary statistics of maximum absolute values, maximum change from baseline, and time to maximum value over the 1-hour period after cocaine infusions. Data will be compared between groups and within groups between study days by Wilcoxon rank sum statistic.

BSCS scores will be presented for each item as n, mean, SD, median, minimum, and maximum values at each scheduled assessment. Group scores will be compared using Wilcoxon rank sum statistic for pre- and post- cocaine infusion assessments.

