## 3.2 Secondary Objectives

Following are the secondary objectives:

- To evaluate whether administration of SXC-2023 alters the pharmacokinetics (PK) of cocaine and/or its major metabolite, benzoylecgonine (BE).
- To determine the PK of SXC-2023 administered at a dose of 800 mg once daily.
- To evaluate whether SXC-2023 treatment alters the subjective effects of cocaine measured by Visual Analog Scales (VAS) and Brief Substance Craving Scale (BSCS).

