#### 7.4.2 Cardiovascular Responses

Summary statistics (n, mean, standard deviation, median, minimum and maximum) of HR and BP by treatment, cocaine dose, infusion session, and timepoint will be presented. Maximum, maximum change and time to maximum from pre-infusion during the first hour after each infusion will be summarized by treatment, cocaine dose, and infusion session.

The maximum value and maximum change from pre-infusion values will be analyzed using an analysis of covariance (ANCOVA) model to compare the treatment groups (SXC-2023 versus placebo). The ANCOVA model will include the baseline (i.e., prior to SXC-2023/placebo treatment) maximum value or the baseline maximum change from pre-infusion as a covariate. The analyses for the 20mg and 40mg cocaine infusions will be performed separately. Effects will be considered statistically significant at a two-sided  $p < 0.05$ .

The distribution of the maximum value and maximum change for HR and BP will be explored. If not deemed normal or if right skewed, an ANCOVA analysis will be performed on the log-transformed HR and BP maximum value and maximum change. If the log-transformed data distribution is not normal then a Wilcoxon rank sum test will be used to compare treatment groups.

Time to maximum value will be analyzed using a Kaplan-Meier estimator. A log-rank test will be used to compare the time to maximum value by treatment groups (SXC-2023 vs Placebo). The analyses for the 20mg and 40mg cocaine infusions will be performed separately. Effects will be considered statistically significant at a two-sided  $p < 0.05$ .

ECG parameters extracted from Holter and their changes from pre-infusion (mean of the 3 pre-infusion ECGs) will be presented with summary statistics by visit and timepoint. Changes in ECG intervals during saline infusion as compared to those taken during cocaine infusions will be also reported as summary statistics. A listing of clinically significant ECG changes will be presented.

Pulse will be summarized by infusion session, timepoint, and treatment group.

Clinically significant ECG values will be presented in listings.

A listing of repeated assessments will be presented.

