#### **7.5.3.1 VAS Responses**

Subjective effects VAS will be presented as summary statistics of maximum values, change from baseline and time to maximum values over 1-hour from the start of the cocaine infusion by treatment group for each question. Data will be compared between groups by Wilcoxon rank sum test. Additionally, within groups comparisons between study days will be done by Wilcoxon signed-rank test. Time to maximum VAS score will be analyzed using a Kaplan-Meier estimator. A log-rank test will be used to compare the time to maximum value by treatment groups (SXC-2023 vs Placebo). Comparisons will be considered statistically significant at a two-sided  $p < 0.05$ . The analyses for the 20mg and 40mg cocaine infusions will be performed separately.

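### SAP 7.5.3.1 calls within-arm VAS changes between study days significant at p < 0.05, but those tests address change over time, not an SXC-2023 effect

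*SAP*

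**What the plan says.** SAP 7.5.3.1 first gives the randomised comparison: "Data will be compared between groups by Wilcoxon rank sum test". It then adds: "Additionally, within groups comparisons between study days will be done by Wilcoxon signed-rank test". After a log-rank test for time to maximum comes the threshold: "Comparisons will be considered statistically significant at a two-sided" p < 0.05. Nothing limits that sentence to the between-arm tests, and nothing marks the within-arm tests as descriptive.

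The section names no pairs of days. It says "The analyses for the 20mg and 40mg cocaine infusions will be performed separately", which implies Day 8 against Day 1 for 20 mg and Day 9 against Day 2 for 40 mg. It also does not say whether the baseline in its change from baseline is the pre-infusion score or the baseline session.

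The objective served (SAP 3.2) is whether SXC-2023 changes cocaine's subjective effects.

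The protocol differs. Section 12.6 on VAS says: "Data will be compared between groups and within groups between study days by Wilcoxon rank sum statistic". Section 12.4.2 on heart rate and blood pressure says: "Data will be compared between groups and within groups by study day by Wilcoxon rank sum statistic". SAP 7.4.2 instead compares arms for heart rate and blood pressure by ANCOVA and lists no within-arm test. It states: "The ANCOVA model will include the baseline (i.e., prior to SXC-2023/placebo treatment) maximum value or the baseline maximum change from pre-infusion as a covariate".

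**The concern.** The session order is fixed. Days 1 and 2 precede the capsules, and Days 8 and 9 fall at the end of the seven-day course. By Day 8 a participant has had three earlier cocaine sessions, and by Day 9 four, all as an inpatient. Tolerance, sensitisation, expectancy or habituation to the setting could each move scores in both arms. The placebo arm is there to remove such a shared change, and a test within the SXC-2023 arm alone makes no use of it.

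The practical risk lies in the report. A within-arm p < 0.05 carries the same label as the randomised result. A pattern of significant with SXC-2023 but not with placebo then invites the conclusion that the drug altered cocaine's effects, when chance and a shared time trend can produce it.

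A second, smaller matter is that the protocol names an independent-samples test for comparisons in which the same participants supply both days.

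**Working it through.** **Inputs from the documents.** 10 randomised and at least 8 completers per arm (SAP 4.2); analysis of participants who completed all five sessions (SAP 6.4 and 7.5.3), so the data are paired; two-sided 0.05. Neither document gives a power, SD or error rate for these tests, so there is no stated figure to reproduce.

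**Assumptions.** Normal scores; a shift d shared by both arms, in units of the single-session SD (0, 0.3, 0.5); correlation r between a participant's two sessions of 0.5 or 0.7; no drug effect.

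**Step 1: size under the test's own null.** Count the sign patterns whose smaller rank total is at or below the critical value.
- n = 8, critical value 3: 2 × 5 / 2^8 = 10/256 = 3.9%.
- n = 10, critical value 8: 2 × 25 / 2^10 = 50/1024 = 4.9%.

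The signed-rank test holds its level when nothing changes between sessions.

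**Step 2: shared shift, no drug effect.** The standardised within-person change is d / √(2(1 − r)). For d = 0.5 this is 0.5/1 = 0.50 at r = 0.5 and 0.5/0.775 = 0.65 at r = 0.7. Simulated rejection rates:

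| n per arm | r | d (SD) | Signed-rank rejects in SXC-2023 arm | Rejects in SXC-2023 arm only | Between-arm rank sum on the change |
|---|---|---|---|---|---|
| 8 | 0.5 | 0 | 4% | 4% | 5% |
| 8 | 0.5 | 0.3 | 9% | 8% | 5% |
| 8 | 0.5 | 0.5 | 19% | 15% | 5% |
| 8 | 0.7 | 0 | 4% | 4% | 5% |
| 8 | 0.7 | 0.3 | 13% | 11% | 5% |
| 8 | 0.7 | 0.5 | 30% | 21% | 5% |
| 10 | 0.5 | 0 | 5% | 5% | 4% |
| 10 | 0.5 | 0.3 | 13% | 11% | 4% |
| 10 | 0.5 | 0.5 | 28% | 20% | 4% |
| 10 | 0.7 | 0 | 5% | 5% | 4% |
| 10 | 0.7 | 0.3 | 19% | 15% | 4% |
| 10 | 0.7 | 0.5 | 43% | 25% | 4% |

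**Step 3: check on the one-arm-only column.** The arms are independent and have the same rejection probability p, so the rate is p(1 − p): 0.30 × 0.70 = 0.21 and 0.43 × 0.57 = 0.25, as simulated. It cannot exceed 25% for a single test.

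**Step 4: the between-arm test.** Its exact attainable size is 4.99% (8 per arm) and 4.33% (10 per arm). It stays near those values at every shift, because the shared shift cancels. A between-arm test of the treatment-day values alone does the same.

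**Step 5: the protocol's rank sum test on paired data.** With no shift it rejects in 1.2% (r = 0.5) or 0.4% (r = 0.7) of trials at n = 8, and in 0.9% or 0.2% at n = 10. It is conservative, because it ignores the positive correlation.

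**The case against.** The drug question already has the right test. The between-arm rank sum test comes first in SAP 7.5.3.1, and the within-arm tests are additional. Signed-rank is the correct procedure for paired data, and detecting a real change between sessions is its purpose. The VAS is a secondary endpoint in a 20-person Phase 1 study whose SAP is mainly descriptive. All of this stands.

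Three stronger readings are tempting, and the documents do not support them.
- *The within-arm tests have an inflated error rate as such.* They do not: the excess over 5% appears only with a shared session-to-session change, and neither document gives its size.
- *The sponsor plans to infer a drug effect from within-arm results.* No passage says so. The problem is a significance label wide enough to permit that inference.
- *The analysis will apply an independent-samples test to paired data.* The SAP uses signed-rank for the VAS and lists no within-arm test for heart rate and blood pressure. What remains is that it does not say it has dropped the protocol's version.

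Multiplicity over the VAS items is a separate question. SAP 7.5.3.1 does not state how many within-arm tests there will be, so no family-wise figure is given here.

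The objection does not remove the main point. The threshold sentence covers both kinds of comparison, and only one of them bears on SXC-2023.

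**Conclusion.** The point holds as a matter of interpretation and labelling; the signed-rank test itself is not at fault. A within-arm rejection cannot separate SXC-2023 from time and repeated cocaine exposure, yet it would be reported as significant on the same terms as the randomised comparison.

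The size depends on a shared change that has to be assumed. At 0.3 to 0.5 SD and correlation 0.5 to 0.7, each SXC-2023-arm test rejects without a drug effect in about 9% to 30% of trials with 8 completers, or 13% to 43% with 10. The misleading one-arm-only pattern occurs in about 8% to 25%. With no shared change, both figures fall to about 4% to 5%. The randomised VAS comparison and the primary heart rate and blood pressure comparison between arms are unaffected.

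The protocol's rank sum wording for same-participant comparisons is wrong, but it errs towards too few rejections, and the SAP's listed analyses do not use it.

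**What to change.** In SAP 7.5.3.1:
1. Limit the p < 0.05 statement to between-arm comparisons.
2. Name the day pairs (dose implies Day 8 with Day 1 and Day 9 with Day 2) and define the baseline. Make the between-arm test include the change from the matching baseline session, or adjust for the baseline-session value as SAP 7.4.2 does for heart rate and blood pressure. Without this step, demoting the within-arm tests could leave the baseline-session VAS data out of every inferential test.
3. Report within-arm changes descriptively with confidence intervals, and state that they will not be used to conclude that SXC-2023 has an effect.

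Add one sentence to the SAP saying that it supersedes the within-group rank sum wording in protocol 12.4.2 and 12.6, and that the within-arm heart rate and blood pressure test is dropped. That is enough; a protocol amendment, which would need IRB approval under protocol 11.3, is not required for this purpose.

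The cost is SAP wording and modest reprogramming, with no new data. The downside is that some within-arm p-values are no longer reported as findings.

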### **7.5.3.2 BSCS Scores**

BSCS scores will be presented for each item as n, mean, SD, median, minimum, and maximum values at each scheduled assessment by treatment group. Group scores will be compared using Wilcoxon rank sum statistic for pre- and post- cocaine infusion assessments.

## **7.6 Other Outcome Measures**

### **7.6.1.1 BDI Scores**

BDI scores will be presented for each item in a listing.

### **7.6.1.2 BAI Scores**

BAI scores will be presented for each item in a listing.

### **7.6.1.3 Mental Status**

Mental status exam findings will be presented in a listing.

## **7.6.2 Tobacco Consumption**

A listing of the cigarette consumption during the trial will be presented.

## **8. TABLES, FIGURES, LISTINGS, AND APPENDICES**

The proposed listing of tables, figures, and listings to be generated with the analysis and included in clinical study report is presented in a separate document.

## APPENDIX A

Table A-1 Schedule and Volume of Blood Collections

	Per sample		Study Day																Total Volume (mL)
			-28 to -4	-3	-2	-1	1	2	3	4	5	6	7	8	9	10	11	18 to 21	
Chemistries (including pregnancy testing and FSH, if needed)	5 mL	S	1	1							1					1		15	
Hematology	4 mL	P	1	1							1					1		12	
PK Samples for cocaine*	4 mL	P						13							13			104	
PK Samples for SXC-2023*	4 mL	P												9	2†	1††		48	
Total (mL)			9	9				52				9			88	8	13	188	
S = Serum, P = Plasma																			
Additional 1 mL of blood will be added to every in-house collection as potential waste due to use of catheter.																			
*For collection, storage, and shipping of PK samples see the study Manual of Procedures (MOP).																			
†24 and 36 hours after SXC-2023 dosing on Day 9																			
††48 hours after SXC-2023 dosing on Day 9
